Name of active ingredient: Olodaterol and Tiotropium Bromide (ATC R03AL06); Umeclidinium and Vilanterol (ATC R03AL03)			
Protocol date: 22 November 2019	Study number: 1237-0090	Version/Revision: 1.0	Version/Revision date: NA
		

• A record for dispensed Olodaterol/Tiotropium Bromide delivered with Respimat inhalator or Umeclidinium/Vilanterol delivered with the Ellipta Inhaler during the 180-day baseline prior to cohort entry.

• Diagnosis of asthma any time prior to cohort entry.

• Diagnosis of lung cancer any time prior to cohort entry.

• Diagnosis of lung transplant any time prior to cohort entry.

	

Name of company: Boehringer Ingelheim International GmbH			
Name of finished medicinal product: Stiolto® Respimat®; Anoro® Ellipta®			
Name of active ingredient: Olodaterol and Tiotropium Bromide (ATC R03AL06); Umeclidinium and Vilanterol (ATC R03AL03)			
Protocol date: 22 November 2019	Study number: 1237-0090	Version/Revision: 1.0	Version/Revision date: NA

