Name of finished medicinal product: Stiolto® Respimat®; Anoro® Ellipta®			
Name of active ingredient: Olodaterol and Tiotropium Bromide (ATC R03AL06); Umeclidinium and Vilanterol (ATC R03AL03)			
Protocol date: 22 November 2019	Study number: 1237-0090	Version/Revision: 1.0	Version/Revision date: NA

Cox proportional hazard regression model will be used to assess the relative rate (or hazard) of the outcome in patients treated with Olodaterol/Tiotropium Bromide compared to patients treated with Umeclidinium/Vilanterol during the one-year follow-up. Crude HRs and 95% CIs will be reported for the matched cohorts.
 
Among the matched cohort, relative risks with 95% CIs will also be reported, as assessed by conditional logistic regression.
 
Relative rates and risks will also be reported using standard multivariable regression.
 
Sensitivity Analyses
 
 
• Restrict the 60-day allowable grace period used to define the discontinuation outcome to 30 days.
 
• Increase the 60-day allowable grace period used to define the discontinuation outcome to 90 days.
 
• Start the patient identification period on 21 May 2015 immediately upon FDA approval.
 
• Exclude patients with ACOS. Patients with asthma only but not COPD are still excluded from cohort.
 
			
Milestones:	
 
- Feasibility assessment Sept 2018 (done)
 
- Draft study protocol Dec 2018
 
- Final study protocol Apr 2019
 
- Results tables available May 2019
 
- 1st Abstract submitted (ERS 2019, ISPOR or AMCP ) Jun 2019
 
- Manuscript submitted Q2 2019
 
		

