## Study timeline for the Primary Study Population

## 9.2.2 Study population

The pre-matched study cohort will consist of patients initiating Olodaterol/Tiotropium Bromide or Umeclidinium/Vilanterol between 17 November 2015 and 31 March 2018.

The following exclusion criteria will then be applied:

Aged <40 years.

Enrolment with medical and pharmacy coverage prior to the cohort entry < 180 days.

Never had COPD diagnosis on the cohort entry date or prior to cohort entry.

A record for dispensed Olodaterol/Tiotropium Bromide delivered with Respimat inhalator or Umeclidinium/Vilanterol delivered with the Ellipta Inhaler during the 180-day baseline prior to cohort entry.

[figure not shown]
Diagnosis of asthma any time prior to cohort entry.

Diagnosis of lung cancer any time prior to cohort entry.

Diagnosis of lung transplant any time prior to cohort entry.

Figure 2

Below depicts the flow diagram of patients.

Diagnosis of COPD (ICD-9: 491.\*, 492.\*, 496.\*; ICD-10: J41.0, J41.1, J41.8, J42.\*, J43.0, J43.1, J43.2, J43.8, J43.9, J44.0, J44.1, J44.9) will be defined as the presence of an inpatient or outpatient claim.

Diagnosis of asthma (ICD-9: 493.\*; ICD-10: J45, J45.20, J45.21, J45.22, J45.90\*, J45.99\*) will be defined as either 1 inpatient claim or 2 outpatient events 30-365 days apart.

Diagnosis of lung cancer (ICD-9: 162.2, 162.3, 162.4, 162.5, 162.8, 162.9, 231.2; ICD-10: C34.00, C34.01, C34.02, C34.10, C34.11, C34.12, C34.2, C34.30, C34.31, C34.32, C34.80, C34.81, C34.82, C34.90, C34.91, C34.92, C7A.090, D02.20, D02.21, D02.22, Z85.118) will be defined as either 1 inpatient claim or 2 outpatient events 30-365 days apart.

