### 9.7.2 Sensitivity Analysis

Four sensitivity analyses will be conducted. For these analyses, in the interest of reducing the number of additional tables, only the descriptive statistics for the matched population ([Annex Table 2](#)), and primary results ([Annex Tables 4](#) and [5](#)) will be reported.

Two sensitivity analyses will be conducted to evaluate the robustness of the outcome definition:

1. Use of a 30-day Grace Period

Restrict the 60-day allowable grace period used to define the discontinuation outcome to 30 days to allow a gap of one month. This sensitivity analysis may be useful if the 60-day grace period is too lenient, as the usual day's supply of Stiolto is 30 days.

2. Use of a 90-day Grace Period

Since neither the Olodaterol/Tiotropium Bromide or Umeclidinium/Vilanterol drug products are available as generic formulations, the relatively high price of these medications may lead some patients to space out their doses to greater than the recommended dosing schedule or use one puff instead of two to prolong their medication supply. Patients may also neglect to take their medications due to forgetfulness or because they become less symptomatic. Thus, we will also increase the 60-day allowable grace period used to define the discontinuation outcome, to 90 days.

Two sensitivity analyses will be conducted in an attempt to increase the sample size:

3. Start Patient Identification Period in 21 May 2015

The primary identification period starts 180 days after Stiolto Respimat was approved by FDA for use in the US (21 May 2015) on 17 November 2015. This sensitivity cohort will start the patient identification period immediately upon FDA approval on 21 May 2015.

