#### 4. Do Not Exclude Patients with Diagnosis of ACOS from the Cohort

Patients in the primary analysis with diagnosis of asthma (regardless of whether or not they have COPD) will be excluded to restrict to patients with only COPD. It is possible that some patients with COPD may have a claim for asthma prior to their COPD diagnosis as part of their COPD diagnostic work-up, rather than an ongoing asthma diagnosis. Therefore, this sensitivity cohort will not exclude patients with a previous diagnosis of asthma. Note that patients with only asthma but no COPD will still be excluded from this cohort.

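### The Abstract gives sensitivity analysis 4 the opposite eligibility rule to Section 9.7.2; correct the Abstract, and balance on prior asthma in that analysis

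*Combined protocol and SAP*

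**What the plan says.** The primary exclusion criteria, in both the Abstract and Section 9.2.2, include "Diagnosis of asthma any time prior to cohort entry". They also remove anyone who "Never had COPD diagnosis on the cohort entry date or prior to cohort entry". In Section 9.2.2 an asthma diagnosis "will be defined as either 1 inpatient claim or 2 outpatient events 30-365 days apart".

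The last bullet under Sensitivity Analyses in the Abstract reads "Exclude patients with ACOS. Patients with asthma only but not COPD are still excluded from cohort".

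Section 9.7.2 introduces analyses 3 and 4 with "Two sensitivity analyses will be conducted in an attempt to increase the sample size". Item 4 is headed "Do Not Exclude Patients with Diagnosis of ACOS from the Cohort". It restates the primary rule, "Patients in the primary analysis with diagnosis of asthma (regardless of whether or not they have COPD) will be excluded", and then sets the sensitivity rule: "this sensitivity cohort will not exclude patients with a previous diagnosis of asthma". Its rationale is that an asthma claim may be part of the work-up that led to the COPD diagnosis. It closes by noting that patients with asthma and no COPD stay out.

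The document is version 1.0 and Section 5 records no amendments, so neither statement is superseded text.

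**The concern.** The two statements give opposite eligibility for the same patient. Of the four sensitivity analyses, two vary the grace period and one moves the start of patient identification. Item 4 is the only one that examines the asthma exclusion, and the protocol gives its own reason to examine it. A reader of the Abstract would take away a rule that appears to repeat the primary restriction.

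A second issue follows once the 9.7.2 rule is applied. Lifting the exclusion lets prior asthma vary between the two arms. Section 9.3.3 lists no asthma covariate and the Table 2 shell has no asthma row. An imbalance on the characteristic that defines the added patients could therefore enter the matched comparison without appearing in the planned tables.

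**Working it through.** No sample size, power or event figure is involved, so the check is a comparison of cohort definitions.

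Take patients who meet every other criterion (new use, age, enrolment, no lung cancer, no lung transplant). Let C be a COPD diagnosis on or before entry and A a prior asthma diagnosis by the Section 9.2.2 algorithm. Read ACOS as C and A together, which is how 9.7.2 item 4 uses it.

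- Primary cohort (Section 9.2.2): C and not A.
- Abstract version of analysis 4: the primary cohort minus (C and A). This is again C and not A, so no patient is removed and none is added.
- Section 9.7.2 version: C, with or without A. This contains the primary cohort and adds everyone with C and A.

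Applied to four kinds of patient:

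| Patient | Primary | Abstract rule | 9.7.2 rule |
|---|---|---|---|
| COPD, no asthma claim | in | in | in |
| COPD, two prior outpatient asthma claims 30-365 days apart | out | out | in |
| COPD, only two prior outpatient asthma claims, ten days apart | in | in | in |
| Asthma, no COPD | out | out | out |

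The second row is where the rules conflict. The third row shows that the spacing requirement matters: two asthma claims alone do not make a patient ineligible. Under the Abstract rule the change in N is 0, which cannot serve the sample-size aim. Under 9.7.2 the change in N is the number with C and A. The documents do not give that number, and the Table 1 shell is blank.

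Next, whether the planned covariates already record asthma. Section 9.3.3 contains inhaled corticosteroid use, LABA/ICS use, allergic rhinitis and hospitalization for a respiratory condition. The code list for the last of these (Annex 4) includes asthma codes, but only as the principal inpatient diagnosis and within the 180-day covariate window. The exclusion counts outpatient diagnoses as well, and the Table 1 shell applies it over all available data. The listed covariates are therefore partial proxies. The asthma flag itself must already be derived in order to apply the primary exclusion.

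**The case against.** The strongest reply is that this is a slip in a synopsis that the body already resolves. The heading, rationale, operative sentence and closing note of 9.7.2 item 4 all agree, as does the stated sample-size aim. In the Abstract's own second sentence, the word *still* makes best sense if ACOS patients are being kept. All of this stands. Someone programming from 9.7.2 would not build the Abstract version.

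A reader might infer something stronger: that the planned analysis will return a hazard ratio identical to the primary one and pass for evidence of robustness. The documents do not support that, for three reasons.

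- Section 9.7.2 requires the matched descriptive table and the result tables for each sensitivity analysis, so an unchanged N would be visible in an analysis meant to enlarge the cohort. Section 9.8 requires a second analyst or scientist to review cohorts and tables.
- ACOS has no definition, code list or abbreviation entry. A looser meaning, such as a single outpatient asthma claim, would make the Abstract version a further restriction. So would one using the J45.3 to J45.5 codes, which Annex 4 lists for respiratory hospitalization but the Section 9.2.2 asthma list omits. No such definition is given, and it would still contradict 9.7.2.
- An identical hazard ratio also requires repeatable matching, and the Matched Cohort text fixes neither match order nor seed.

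On the covariate, the objection is that it goes beyond the contradiction, that no imbalance has been shown, and that changing the propensity model mixes a model change with a cohort change. It is correct that no imbalance is shown and that the model would differ. Even so, asthma is constant by definition in the primary cohort and free to vary in this one, which is reason enough to balance on it and report it.

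**Conclusion.** The contradiction is real and lies in the current text. The Abstract bullet is wrong as a description of analysis 4, most likely through a dropped *Do not*. If ACOS means COPD plus asthma by the Section 9.2.2 algorithm, the Abstract version removes nobody beyond the primary exclusion and cannot test it.

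The consequence is limited. The primary cohort and primary estimate are untouched, and 9.7.2 is clear enough to work from. The point is worth correcting because the Abstract states an analysis rule that is the opposite of the intended one, and because the intended cohort lacks a direct measure of the characteristic it newly admits. How far the hazard ratio would move under 9.7.2, and how many patients would be added, cannot be determined from the documents.

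**What to change.** 1. Replace the Abstract bullet with the 9.7.2 rule, for example: COPD patients who also have an asthma diagnosis are not excluded; patients who have asthma without COPD remain excluded.

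2. For this sensitivity analysis only, add prior asthma (yes/no) to the propensity score and to the matched Table 2. Use the Section 9.2.2 definition with all available look-back, and state this as an explicit exception to the 180-day covariate window in Section 9.3.3.

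The cost is one corrected Abstract bullet, one sentence in 9.7.2, one table row and one covariate that the primary exclusion already requires. The small downside is that the propensity model for this analysis differs from the primary model by one term. A change in the hazard ratio could then reflect the added patients, the added covariate or both, and the report should say so where the two estimates are compared.

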## 5. AMENDMENTS AND UPDATES

Not Applicable

## 6. MILESTONES

Milestone	Planned Date
Draft Protocol	17 December 2018
Protocol Revisions	22 February 2019*
Start of Implementation	01 March 2019
Preliminary Result Tables	15 March 2019
Final Result Tables and Documentation of Implementation	26 April 2019

\*Pending time for approval and suggested changes proposed by BI

## 7. RATIONALE AND BACKGROUND

Chronic obstructive pulmonary disease (COPD) is a common disease characterized by airway obstruction confirmed by spirometry, often including small airway obstruction, chronic bronchitis and emphysema (**Barnes 2015**). No known medications can reverse COPD, but regular maintenance treatments can help manage symptoms, reduce frequency of COPD exacerbations and improve health-related quality of life. Inhaled therapies are the cornerstone of COPD disease management approaches. The aim of inhaled therapy is to deliver agents directly to the lungs, thereby offering benefits while minimizing the potential for treatment-related adverse effects (**Braido 2016**).

Adherence to obstructive lung disease therapies involves patients initiating their prescribed therapy, implementing it as prescribed (i.e. correctly administering the prescribed dose at the physician directed frequency), and persisting with treatment (**Braido 2016; Mäkelä 2013**). Central to the therapeutic benefit of inhaled therapies is their successful administration which requires patients to have knowledge and understanding of (and ability to implement) the appropriate inhaler technique required to optimize both the dispensed and administered doses (**Braido 2016**). Inspiratory capabilities of patients with COPD are affected by increasing static and dynamic hyperinflation and weakening of the respiratory muscles, causing many patients to have peak inspiratory flow rates that are suboptimal to use many dry-powder inhalers (DPIs) (**Sohini 2017**). This paradoxical situation may lead to improper inhalation that prevents successful drug delivery to the lungs, which may affect treatment effectiveness. On the other hand, soft mist inhalers (SMI) force a metered dose of drug solution through a precise nozzle to deliver consistent and reliable doses to the lungs with each actuation (**Dalby 2004**) and may help preserve benefits in patients with diminished peak inspiratory flow rates.

Stiolto® Respimat®, a combination of Olodaterol and Tiotropium Bromide delivered via soft mist inhaler (SMI), was approved in May 2015 in the US and July 2015 in the EU (marketed

as Spiolto in the EU). Anoro® Ellipta®, a combination of Umeclidinium and Vilanterol delivered via dry powder inhaler (DPI), was approved in December 2013 in the US and in February 2014 in the EU. Both products are maintenance therapies consisting of a combination of long-acting muscarinic antagonists (LAMA) and long-acting beta agonists (LABA). However, the question of whether different devices (DPI and SMI) play a role in treatment persistence remains to be answered.

This study seeks to compare the treatment persistence of two drugs in same drug class (LAMA/LABA as a fixed dose combination [FDC]) delivered through different devices (a DPI and a SMI) within an administrative claims database in the US.

## **8. RESEARCH QUESTION AND OBJECTIVES**

The primary objective of the study is to use US data to determine relative treatment persistence in using Olodaterol/Tiotropium Bromide delivered with the Respimat soft mist inhaler and Umeclidinium/Vilanterol delivered with the Ellipta dry powder inhaler using a 1:2 propensity score matched analysis.

The secondary objectives of the study are as follows:

Characterize new users of Olodaterol/Tiotropium Bromide and Umeclidinium/Vilanterol in terms of demographics, medication use, comorbidities, and other variables, before and after propensity score matching.

Determine the rate and proportion of patients discontinuing among new users of Olodaterol/Tiotropium Bromide and Umeclidinium/ Vilanterol.

Determine the relative rate and proportion of patients discontinuing between Olodaterol/Tiotropium Bromide and Umeclidinium/Vilanterol, using a standard multivariate analysis (If feasible).

## **9. RESEARCH METHODS**

### **9.1 STUDY DESIGN**

The proposed study will utilize data from the Truven MarketScan dataset (US).

The Truven MarketScan databases are comprised of two components: the MarketScan Commercial Claims and Encounters (CCAE) Database and the Medicare Supplemental and Coordination of Benefits (COB) Database. These databases capture longitudinal, individual-level data on healthcare utilization, healthcare expenditures and plan enrollment, and contain integrated records for patient demographics, inpatient events, outpatient events, and pharmacy dispensing of drugs. The CCAE database is a medical and drug insurance claims database on ~150 million patients since from 2008 unique de-identified patients that include active employees, dependents, retirees or recipients of the Consolidated Omnibus Budget Reconciliation Act (COBRA), and data are drawn from large employers, health plans, and public organizations in the United States (Truven Health MarketScan® Research Databases 2015). The MarketScan Medicare Supplemental and Coordination of Benefits (COB) Database contains pooled medical and drug insurance claims data of approximately 13.6 Million unique de-identified patients (since 1996) that are Medicare-eligible retirees with employer-sponsored Medicare Supplemental plans. (**Truven Health MarketScan® Research Databases 2015**).

In principle, in US when a patient goes to a pharmacy and gets a drug dispensed, the pharmacy bills the insurance carrier for the cost of that drug (**Strom 2013**). For billing purposes, the pharmacy has to identify which medication was dispensed along with the dosage strength (e.g. the milligrams per tablet) and quantity (e.g., number of tablets, etc.). Analogously, when a patient goes to a hospital or to a physician for medical care, the providers of care bill the insurance carrier for the cost of the medical care, and have to justify the bill with a diagnosis. Using a common patient identification number for both the pharmacy and the medical care claims, these elements can be linked, and analyzed as a longitudinal medical record (**Strom 2013**).

### **9.2 SETTING**

#### **9.2.1 Definitions**

Study Period: the period of time that includes the exclusion criteria assessment period, baseline, cohort entry date, and follow-up period for the study population. This period is the same for all patients.

The study period will be from 1 January 2008 to 31 March 2018, encompassing date of the earliest data availability to the date of the latest data availability.

Patient Selection Period: the period of time for which patients are eligible to enter the cohort. The earliest date of the patient selection period is 17 November 2015, corresponding to 180-days after US approval date of Stiolto Respimat.

Cohort Entry Date: Date of entry to the initial cohort of Stiolto or Anoro users.

[figure not shown]
Baseline Period: the 180-day period that ends 1 day prior to the cohort entry date used to assess covariate information. The baseline period will vary between patients depending on these dates. The earliest start of the baseline period would be 21 May 2015, the date of Stiolto approval (i.e. 180 days before November 17, 2015).

Follow-Up Period: the period of time between 1 day after the cohort entry date to the earliest occurrence of the outcome (discontinuation of refills), or any censoring criteria (365 days, death, disenrollment, or end of data). Addition of another treatment in addition to index treatment will not count as discontinuation.

For entry into the study population, patients will be required to have 180 days of continuous enrolment with both medical and pharmacy coverage. Data during the baseline period will be used to confirm study eligibility and classification of incident COPD. The follow-up period will be used for capturing first and second maintenance therapies. This is illustrated in **Figure 1**.

Figure 1

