### Matched Cohort

A matched propensity score analysis will be used to assess comparative persistence between the two exposure comparison groups. Logistic regression will be used to calculate the propensity to initiate Olodaterol/Tiotropium Bromide versus Umeclidinium/Vilanterol given all covariates (except components of the Charlson Comorbidity index) listed in [section 9.3.3](#), according to the following model:

$$\text{Logit}(\text{Treatment} | X_1, X_2, \dots, X_n) = \beta_0 + \beta_1 * X_1 + \beta_2 * X_2 + \dots + \beta_n * X_n$$

Any covariates which are collinear with each other will be dropped from the analysis (if it causes failure of model to converge). The propensity score will then be used to identify up to 2 initiators of Umeclidinium/Vilanterol for each initiator of Olodaterol/Tiotropium Bromide with the same propensity score ( $\pm$  a caliper of 5%) as the corresponding initiator of Olodaterol/Tiotropium Bromide (Austin 2011).

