#### 9.7.1.3 Comparative Persistence

- Relative Rate of Discontinuation of Olodaterol/Tiotropium Bromide vs Umeclidinium/Vilanterol in the Unmatched Cohort

Multivariable Cox proportional hazards models with all variables (except components of the Charlson Comorbidity index) in [section 9.3.3.](#) will be used to estimate the hazard ratios (HRs) and 95% CIs for Olodaterol/Tiotropium Bromide compared to patients treated with Umeclidinium/Vilanterol during follow-up for incident discontinuations, according to the following model:

$$h(t | \text{Treatment}, X_1, \dots, X_n) = h(t_0) * \exp(\beta_1 * \text{Treatment} + \beta_2 * X_2 + \dots + \beta_n * X_{n+1})$$

Where treatment can be 1=Stiolto or 0=Anoro and t = time to discontinuation

- Relative Risk of Discontinuation of Olodaterol/Tiotropium Bromide vs Umeclidinium/Vilanterol in the Unmatched Cohort

Multivariable logistic regression will be used to assess relative risk of discontinuation and 95% CIs for Olodaterol/Tiotropium Bromide compared to patients treated with Umeclidinium/Vilanterol during follow-up for incident discontinuations, according to the following model using all covariates (except components of the Charlson Comorbidity index) in [section 9.3.3.](#):

$$\text{Logit}(\text{Discontinuation}=1 | \text{Treatment}, X_1, X_2, \dots, X_n) = \beta_0 + \beta_1 * \text{Treatment} + \beta_2 * X_2 + \dots + \beta_n * X_{n+1}$$

- Relative Rate of Discontinuation of Olodaterol/Tiotropium Bromide vs Umeclidinium/Vilanterol in the Matched Cohort

Cox proportional hazards models with treatment as the only independent variable will be used to estimate the hazard ratios (HRs) and 95% CIs for Olodaterol/Tiotropium Bromide

compared to patients treated with Umeclidinium/Vilanterol during follow-up for incident discontinuations, according to the following model:

$$h(t | \text{Treatment}, X) = h_0(t) * \exp(\beta_1 * \text{Treatment})$$

Where treatment can be 1=Stiolto or 0=Anoro and t = time to discontinuation

- Relative Risk of Discontinuation of Olodaterol/Tiotropium Bromide vs Umeclidinium/Vilanterol in the Matched Cohort

Logistic regression will be used to assess relative risk of discontinuation and 95% CIs for Olodaterol/Tiotropium Bromide compared to patients treated with Umeclidinium/Vilanterol during follow-up for incident discontinuations, according to the following model:

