## **ANNEX 5. TABLE SHELLS AND PROPOSED FIGURES**

**Table 1.** Cohort Selection

	Excluded	Remaining
Eligible Population		
Did not meet cohort entry criteria (use of Tio/Olo or Ume/Vi)		
< 180 days of continuous enrollment		
Prior use of Ume/Vi during 180d washout		
Prior use of Tio/Olo during 180d washout		
Tio/Olo and Ume/Vi both occurring on cohort entry date		
Age <40 years		
No prior diagnosis of COPD any time prior using all available data		
Diagnosis of Asthma any time prior using all available data		
Diagnosis of Lung Cancer any time prior using all available data		
Lung Transplant any time prior using all available data		
Final cohort		

**Table 2.** Patient Characteristics of the Study Population (Unmatched/ Matched)

	Tio/Olo	Umech/Vi	Standardized Difference (95% CI)
N			
Median Follow-up Time [IQR]			
Demographics			
Age on index date			
Mean (SD)			
Median [IQR]			
Gender			
Male; n (%)			
Female; n (%)			
Region			
Northeast; n (%)			
North Central; n (%)			
South; n (%)			
West; n (%)			
Missing/Unknown; n (%)			
Insurance Type			
Commercial; n (%)			
Medicare; n (%)			
Missing; n (%)			
Year of Cohort Entry, n (%)			
First Year (November 17, 2015 – November 30, 2016); n (%)			
Second Year (December 1, 2016 – November 30, 2017); n (%)			
Third Year (December 1, 2017 to March 31, 2018)			
Concomitant Medications			

Proprietary confidential information © 2019 Boehringer Ingelheim International GmbH or one or more of its affiliated companies

	Tio/Olo	Umec/Vi	Standardized Difference (95% CI)
Oral Corticosteroids; n (%)			
Short acting muscarinic antagonist (SAMA), n (%)			
Short acting beta agonist (SABA), n (%)			
Long acting muscarinic antagonist (LAMA), n (%)			
Long acting beta agonist (LABA), n (%)			
Inhaled corticosteroid (ICS), n (%)			
LAMA / LABA combination (not Tio/Olo or Umec/Vi), n (%)			
LABA / ICS combination, n (%)			
LAMA / LABA / ICS combination, n (%)			
NSAIDs, n (%)			
Antihistamines, n (%)			
Opioids, n (%)			
Oral antibiotics, n (%)			
Antidiabetic Agents (not including insulin), n (%)			
Insulin (basal or mealtime), n (%)			
Methotrexate, n (%)			
Statins; n (%)			
Antihypertensives; n (%)			
Anticoagulants; n (%)			
Anti-psychotic/anti-depressives/anxiolytic, n (%)			
Oxygen therapy, n (%)			
Comorbidities/Symptoms			
History of All-Cause Hospitalization; n (%)			
History of Emergency Department Visit; n (%)			

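### Section 9.2.1 announces a classification of incident COPD that is undefined, cannot be made from the 180-day baseline alone, and enters no covariate list, model or table, so newly diagnosed and long-standing COPD are not directly balanced or checked

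*Combined protocol and SAP*

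**What the plan says.** Section 9.2.1 assigns the baseline data two jobs: "Data during the baseline period will be used to confirm study eligibility and classification of incident COPD". The same section defines the baseline as "the 180-day period that ends 1 day prior to the cohort entry date used to assess covariate information".

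Eligibility takes in COPD of any duration. Section 9.2.2 excludes a patient only for "Never had COPD diagnosis on the cohort entry date or prior to cohort entry", and the corresponding row of Table 1 in Annex 5 searches the whole record: "No prior diagnosis of COPD any time prior using all available data". Section 9.4 gives data from January 2008.

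Confounder control rests on one list. The propensity score is fitted "given all covariates (except components of the Charlson Comorbidity index) listed in" section 9.3.3. The unmatched analysis uses "Multivariable Cox proportional hazards models with all variables (except components of the Charlson Comorbidity index) in" the same section, and the unmatched logistic model does likewise. In the matched cohort, "Cox proportional hazards models with treatment as the only independent variable will be used"; the matched logistic model adds only the matched-set term.

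**The concern.** The plan commits to a patient classification and then gives it no definition and no use. That matters beyond tidiness, because the cohort mixes a patient whose only COPD code falls on the entry date with a patient coded for years.

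Time since diagnosis could plausibly affect both which product is started and how soon refills stop; a provisional diagnosis, for example, may be followed by early stopping. The matched Cox model has no covariates, so any imbalance in disease duration that remains after matching carries into the primary hazard ratio. Because Tables 2 and 3 have no row for it, a reader could not tell whether such an imbalance exists.

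**Working it through.** **1. Where the classification could appear**

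- Covariates (abstract and section 9.3.3): no incident or prevalent COPD term, and no time since first COPD claim.
- Annex 4: no definition of incident COPD. The nearest item is the COPD component of the Charlson-Deyo index, which scores 1 for a COPD event within 180 days. A new diagnosis and a repeat claim in an established patient both score 1, and the point is then summed into a total.
- Models (section 9.2.2, Matched Cohort, and section 9.7.1.3): only section 9.3.3 terms, treatment, or the matched set.
- Table shells 1 to 5: no row.
- Sensitivity analyses (section 9.7.2): none concerns COPD duration.

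Figures 1 and 2 were not available in the text I worked from. A figure might mention the classification, but the models and tables are readable and do not contain it.

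**2. Whether it can be made as written**

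A COPD claim inside the 180-day baseline shows that COPD was coded recently, not that it was coded for the first time. The baseline also ends the day before entry, so it misses a patient whose COPD is newly coded on the entry date, which section 9.2.2 accepts. Section 9.3.3 extends the covariate window to the index date, but that still does not separate new COPD coding from repeat coding. Only the longer look-back, already used for eligibility, can do so.

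**3. Illustrative size**

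The cohort figures reconcile: 3,889 + 10,862 = 14,751 (section 9.5). A full 1:2 match needs 2 × 3,889 = 7,778 comparators, giving at most 3,889 + 7,778 = 11,667 matched patients.

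The documents give no split by disease duration, no effect of duration on discontinuation and no expected number of discontinuations. The following are my assumptions:

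- proportion newly diagnosed *after matching*: p1 = 25% or 30% in one arm, p0 = 20% in the other;
- hazard effect of new diagnosis: R = 1.2 or 1.5;
- proportion discontinuing: 60%, with 30% as a lower case.

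Approximate bias factor: B = [1 + p1(R − 1)] / [1 + p0(R − 1)].

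Standard error of the log hazard ratio with d events and 1:2 allocation: SE = 1/√(d × 1/3 × 2/3).

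- 60% discontinuing: d = 0.6 × 11,667 ≈ 7,000, SE ≈ 0.0254.
- 30% discontinuing: d = 0.3 × 11,667 ≈ 3,500, SE ≈ 0.0359.

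| p1 v p0 | R | B | ln B | ln B / SE, 60% | ln B / SE, 30% |
|---|---|---|---|---|---|
| 25% v 20% | 1.2 | 1.05/1.04 = 1.010 | 0.0096 | 0.38 | 0.27 |
| 25% v 20% | 1.5 | 1.125/1.10 = 1.023 | 0.0225 | 0.89 | 0.63 |
| 30% v 20% | 1.2 | 1.06/1.04 = 1.019 | 0.0190 | 0.75 | 0.53 |
| 30% v 20% | 1.5 | 1.15/1.10 = 1.045 | 0.0445 | 1.75 | 1.24 |

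All these shifts lie inside the half-width of a 95% interval (1.96 SE). Incomplete matching would raise the SE and lower the ratios further. If the newly diagnosed were commoner in the other arm, the shift would go the other way; the documents do not indicate a direction.

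**The case against.** A reader might infer that disease duration is left wholly unbalanced and that the primary hazard ratio is therefore biased. The documents do not support that. The score already contains prior LAMA, LABA, ICS and their combinations, so recent maintenance treatment, and with it step-up within 180 days, is measured directly. It also contains oral corticosteroids, oxygen, respiratory hospitalisation, chronic bronchitis, breathlessness, lung function tests and chest imaging. These may balance disease stage in part. Both products are LAMA/LABA combinations, and nothing in the documents shows that the choice between them depends on time since diagnosis. This objection stands, and it limits the point to balance that is neither direct nor checked.

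The sentence may also be left over from another protocol. The next one, on capturing first and second maintenance therapies during follow-up, matches no listed objective or outcome. If so, deleting it would cure the inconsistency, but COPD duration would still be uncontrolled. Section 9.9 concedes residual confounding only in general terms and does not name it.

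Finally, the obvious remedy is imperfect. Only 180 days of prior enrolment are required, so a patient with the minimum has almost no earlier data in which an older claim could appear and would be called incident almost by construction. A look-back-length covariate does not correct the individual misclassification. The documents give no enrolment distribution, so its extent is unknown. This must be stated and checked, but it does not justify leaving the term undefined.

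**Conclusion.** The point holds in a limited form. The plan announces an incident COPD classification that it does not define, that cannot be derived from the stated window alone, and that no analysis or table uses. New and long-standing COPD are consequently not directly balanced or checked, though proxies in the score may balance them in part.

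On the assumptions above, the hazard ratio would shift by a factor of about 1.01 to 1.05, or roughly 0.4 to 1.8 standard errors at 60% discontinuing and 0.3 to 1.2 at 30%. The upper end needs a ten-point imbalance that survives matching. The true shift may be negligible, and no change of conclusion has been shown. The case for acting is that the variable can be derived from claims already searched, and that nothing now planned would reveal an imbalance in it.

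**What to change.** 1. In section 9.2.1, define incident COPD as a first COPD claim, in all available data up to and including the entry date, that falls within the last 180 days (entry date included). All other patients are prevalent.
2. Add this indicator, or categories of time since first COPD claim, together with length of available look-back, to section 9.3.3. They then enter the propensity score and both unmatched multivariable models.
3. Add matching rows to Tables 2 and 3.
4. State that patients with short prior enrolment may be misclassified as incident, and check this among patients with longer look-back.
5. If the sponsor does not intend to use the classification, delete the sentence and name COPD duration as an uncontrolled confounder in section 9.9.

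The cost is modest: a few derived covariates from claims already searched for eligibility, extra table rows and one check. The alternative in item 5 costs only text but leaves the confounder uncontrolled.
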